3.2.5. Treatment Periods

Period	Definition	
Pre-treatment	Date of Screening through one day prior Date of first dose	
Double-blind	Date of first dose through to Date of last dose during Part A	
Treatment Period	or	
	Date of first dose through to one day prior first dose during open-label treatment	
	period	

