3.5. Rationale for Study Duration, Dosing Regimens, and Design

3.5.1. Justification for Study Design and Duration

The 24-week Treatment Period duration was selected in order to assess the effects of exposure of PTC857 on efficacy, safety, and biomarker activity. The study should provide robust data on the risk/benefit profile of PTC857 for the treatment of subjects with ALS.

The Treatment Period duration of 24 weeks was selected based on the following reasons:

- This duration of evaluation is considered appropriate to demonstrate statistically and/or clinically meaningful drug effects and/or potential trends over placebo on disease progression.
- This duration of evaluation is considered adequate to provide a better understanding of the safety and tolerability of PTC857 compared with placebo.
- This duration of evaluation is considered minimally sufficient to provide a better understanding of the relationship between effects on biomarker activity and clinical efficacy of PTC857.

The LTE Period duration of 28 weeks was chosen to provide for a total of 52 weeks of continuous treatment without interruption between the Treatment and LTE Periods with PTC857

to allow for adequate duration to evaluate the long-term safety, tolerability, efficacy, and biomarker effects of PTC857.

The Continued LTE Period duration was chosen to ensure that subjects have the opportunity to continue to receive PTC857 for an additional 108 weeks for continuing assessments of long-term safety and efficacy.

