7. STUDY ASSESSMENT AND PROCEDURES

The scheduled timepoints and study parameters are delineated in the Schedule of Assessments (Table 1 [Part A], Table 2 [Part B], and Table 3 [Part C]).

In case several study procedures are scheduled at the same timepoint, the following sequence should be followed predose: 12-lead ECG, vital signs, PK blood sampling, and blood sampling for clinical laboratory tests. Likewise, for post-dose, the following sequence should be followed: 12-lead ECG, vital signs, PK blood sampling, and blood sampling for clinical laboratory tests.

During the Day 1, Day 85, and Day 169 Visits, the following testing clinical measures should be performed predose: ALSFRS-R, PFTs, ALS CBS, Modified Norris Scale, C-SSRS, and ALSAQ-40. The ALSFRS-R should be the first test performed; all other tests may be performed in any order.

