Laboratory data will be summarized descriptively by visit for each laboratory parameter by treatment group and overall. Both observed results and changes from baseline will be summarized for continuous variables. Laboratory values will be categorized as clinical grade (low/normal/high) according to normal ranges. Shifts from baseline to the last on-treatment grade and the worst on-treatment grade will be presented. For these shift summaries, for the last on-treatment summary only scheduled visits will be taken; for the worst on-treatment summaries unscheduled assessments will be included in the assessment of worst. Both worst low and worst high will be summarized.

Laboratory values that are below the limit of quantification will be imputed as the lower-limit of quantification, similarly, values above the limit of quantification will be imputed as the upper-limit of quantification for the summary statistics. But for listings, the values will be presented as recorded.

By-subject listings of all the laboratory parameters will be presented that clearly indicate out of normal range values and possible abnormal values for the safety analysis set.

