6.7. Columbia-Suicide Severity Rating Scale

The C-SSRS is a questionnaire that prospectively assesses suicidal ideation and suicidal behavior (Posner 2011). The C-SSRS, which uses a semi-structured interview to probe subject responses, is administered by an individual who has received training and certification in its administration. During the Screening Visit (Day -56), the "baseline" version of the C-SSRS is administered. This

version assesses suicidal ideation and suicidal behavior during the subject's lifetime. At all subsequent visits, the "since last visit" version is administered.

Counts and percentage of subjects who experience suicidal ideation, suicidal behavior or neither (no ideation or behavior) will be summarized by treatment group at baseline and double-blind treatment period.

The C-SSR instrument consists of 11 Yes/No questions as shown in the table below and is grouped by type question, i.e., suicidal ideation questions and suicidal behavior questions. Within each type/group the questions are re-ordered by increasing severity. In addition, subjects are assessed for any self-injurious behavior without suicidal intent.

C-SSRS Item	Derivation
Suicidal ideation	 A "yes" answer to any one of the following five questions. Wish to be dead. Non-specific active suicidal thoughts. Active suicidal ideation with any methods (not plan) without intent to act. Active suicidal ideation with some intent to act, without specific plan. Active suicidal ideation with specific plan and intent.
Suicidal behavior	A "yes" answer to any one of the following five questions. Preparatory acts or behavior Aborted attempt Interrupted attempt Actual attempt Suicidal behavior Completed suicide
Self-injurious behavior without suicidal intent	A "yes" answer to the following question from suicidal behavior section on the C-SSRS: Has subject engaged in Non-Suicidal Self-Injurious behavior?
Suicidal Ideation Score	Is defined as the maximum suicidal ideation category (1-5 on the C-SSRS) present at the assessment. A score of 0 is assigned if no ideation is present.

For the overall assessment of suicidal ideation and behavior during the double-blind treatment period a subject's worst finding during that period will be used.

The following tables will be generated at the end of the Double-Blind Treatment Period:

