3.2.6. Study Treatment Periods

Period	Definition
Pre-treatment Period	Date of Screening through one day prior Date of first dose
Double-blind	Date of first dose through one day after Date of last dose

Treatment Period	OR
	Date of first dose through one day prior first dose during open-label treatment
	period
Open label Long-	Date of first dose during open-label LTE period (Part B) to Date of last dose
term Extension	during open-label LTE period (Part B or C) plus one
Periods	OR
	Date of first dose during open-label LTE period (Part B) through one after Date of
	last dose during open-label continued-LTE period (Part C)

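### Read literally, the Part A SAP's date rule for the double-blind period can drop the predose Day 169 C-SSRS form and pass it to open-label PTC857; laboratory shifts are exposed only if on-treatment means that period

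*SAP*

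**What the plan says.** Part A SAP 3.2.5 defines the double-blind treatment period by calendar date, with two alternatives joined by a bare *or*:

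- "Date of first dose through to Date of last dose during Part A"; or
- "Date of first dose through to one day prior first dose during open-label treatment" period.

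It does not say which subjects each alternative covers, and it gives no time-of-day rule.

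Parts B/C SAP 3.2.6 defines the same period again. Its second alternative matches, but its first reads "Date of first dose through one day after Date of last dose". It starts the open-label period on the date of the first open-label dose.

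Two kinds of safety output in the Part A SAP look across visits:

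- **C-SSRS (6.7).** Subjects are counted over the double-blind treatment period, and for the overall assessment a subject's "worst finding during that period will be used".
- **Laboratory shifts (6.3).** "Shifts from baseline to the last on-treatment grade and the worst on-treatment grade will be presented". On-treatment is not defined.

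On timing, Protocol section 7 says: "During the Day 1, Day 85, and Day 169 Visits, the following testing clinical measures should be performed predose". The C-SSRS is on that list. Protocol 3.5.1 describes 52 weeks of "continuous treatment without interruption between the Treatment and LTE Periods with PTC857".

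**The concern.** The Day 169 visit is the Week 24 visit, and its findings reflect double-blind treatment. If open-label dosing starts later on the same date, a rule that stops the day before shuts those findings out of the period they describe. Part A SAP 3.2.2 has a same-day rule for baseline measurements, but there is no counterpart at the end of the period.

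Two things are at stake. The period-level C-SSRS tables in the Part A report could omit the last form. In the extension tables, a finding that arose on placebo could be labelled as arising on open-label PTC857. Parts B/C SAP 3.3 includes available extension safety data in the interim report at the Part A lock, so the misattribution could appear there.

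**Working it through.** **1. The plan's own day number.** Week 24 visit = 1 + 24 × 7 = Day 169, as in Protocol Table 1. Twenty-four weeks of dosing therefore covers Days 1 to 168.

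**2. When is the first open-label dose?** No passage states the date. Four point to the Day 169 visit date:

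- Part B consent is signed at that visit (Protocol Table 1 footnotes).
- Part B drug is dispensed at that visit (Protocol Table 2).
- Treatment is uninterrupted (Protocol 3.5.1 and 7.3.15).
- Parts B/C SAP 3.2.2 sets Day 169 as week 0 of PTC857 exposure for subjects who had placebo.

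**3. Scheduled post-baseline assessments (Protocol Table 1).**

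- C-SSRS: Days 29, 57, 85, 113, 141, 169 (six forms).
- Full laboratory panels: Days 29, 57, 85, 169 (Day 14 is lipids only).

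**4. Applying the date rules.**

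| Case | Period ends | Last C-SSRS in period | Last full panel in period |
|---|---|---|---|
| LTE entrant, first open-label dose Day 169 | Day 168 | Day 141 | Day 85 |
| LTE entrant, first open-label dose Day 170 | Day 169 | Day 169 | Day 169 |
| Non-entrant, last dose Day 168, Part A SAP | Day 168 | Day 141 | Day 85 |
| Non-entrant, last dose Day 168, Parts B/C SAP first alternative | Day 169 | Day 169 | Day 169 |
| Non-entrant, last dose Day 169, Part A SAP | Day 169 | Day 169 | Day 169 |

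The laboratory column applies only if on-treatment is read as the 3.2.5 period.

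**5. C-SSRS.** The counts and worst finding in 6.7 use the defined period. In the first and third rows they lose 1 of 6 forms (1/6 = 17%), and the last form kept is 169 − 141 = 28 days before the end-of-treatment visit.

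**6. Assignment to open-label.** Day 169 uses the since-last-visit version of the C-SSRS, and the previous form is Day 141. A predose Day 169 form from a placebo subject therefore reports only on placebo time. Under Parts B/C SAP 3.2.6 its date falls in the open-label period, and section 6.8 of that SAP takes the worst finding over the extension periods.

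**7. Laboratory shifts, under that reading only.** The last scheduled full panel moves from Day 169 to Day 85, which is 169 − 85 = 84 days earlier, or 84/168 = 50% of the treatment days. This applies to the last on-treatment table, which takes scheduled visits only. The worst on-treatment table also admits unscheduled results, so laboratory values from Days 86 to 168 can still enter it.

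**8. Outputs that do not use the rule.**

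- By-visit summaries use the nominal visit.
- The two C-SSRS shift tables run through Week 24 (6.7).
- Adverse events have their own rule (6.2).
- Efficacy uses visit windows, with Day 169 covering Days 155 to 182 for the ALSFRS-R (4.9).

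**The case against.** The strongest reply is that other text already places Day 169 in Part A:

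- Part A SAP 6.3 lists the Day 169 laboratory tests among those collected during the double-blind period.
- The C-SSRS shift tables reach Week 24.
- Day 169 in the Part B schedule has only consent, drug dispensing and a mammogram, so the Day 169 C-SSRS form belongs to the Part A schedule.
- Parts B/C SAP 3.2.2 treats Day 169 as the pre-exposure reference.
- The C-SSRS count tables in Parts B/C SAP 6.8 name the double-blind and extension periods together.
- For LTE entrants the two SAPs agree on the end date; only the alternative based on the last dose differs.
- For non-entrants, the protocol calls the Day 169 measures predose without restricting this to LTE entrants. A double-blind dose that day is possible and would keep the visit.

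Much of this stands. It shows that the intention is probably to keep Day 169 in Part A, and it limits the reach of the problem. It does not cure the rule. The 6.3 list also names Day 183, a Part B visit, so it cannot serve as a period definition. The C-SSRS period counts use the defined term, and no sentence overrides 3.2.5 for them.

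A reader might infer that the laboratory shift tables definitely stop before Week 24, and that half the treatment period is missing from both. The documents do not support that. On-treatment is never tied to 3.2.5, 6.3 points the other way, and the worst table includes unscheduled results.

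**Conclusion.** The rule as written gives a wrong assignment where a predose Day 169 assessment shares its date with the first open-label dose. The direct effect is on the C-SSRS double-blind counts and worst finding, which lose 1 of 6 post-baseline forms, and on the extension period, where a former placebo subject's form can be counted under PTC857. For non-entrants, a Day 169 visit after the last dose date is excluded by the Part A SAP; the first alternative in the Parts B/C SAP would keep it if it falls one day later.

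The laboratory effect is conditional. The last on-treatment scheduled panel would be Day 85 only if on-treatment means the 3.2.5 period, which would contradict 6.3.

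The conclusion rests on a literal reading of 3.2.5 and, for LTE entrants, on a first open-label dose on the Day 169 visit date. A first dose on Day 170 removes the problem. The documents do not say how many subjects will be affected. It would be too strong to infer that Week 24 safety data are lost from the report: by-visit tables and listings keep them, and the primary analysis does not depend on the rule. The outputs at issue are descriptive, but they are the ones meant to show the worst finding over the period.

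**What to change.** Use identical text in Part A SAP 3.2.5 and Parts B/C SAP 3.2.6:

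1. For LTE entrants, assign assessments made before the first open-label dose on that date to the double-blind period, and start the open-label period after them.
2. For non-entrants, state that the Day 169 visit belongs to Part A.
3. Say which alternative applies to which subjects.

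In Part A SAP 6.3, define on-treatment by reference to that period and remove the Day 183 entry from the list of double-blind visits.

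With this text, the last C-SSRS form and the last scheduled full panel are both Day 169 in every case in the table above. The cost is wording in two period tables and one laboratory section, plus the matching derivation. No new data are needed. Where the dose time is not recorded, the protocol's predose scheduling of the C-SSRS can serve as the stated default.

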3.2.6. Coding Dictionary

Where applicable, safety data will be coded using the following coding dictionaries:

Dictionary	Version	
Medical Dictionary for Regulatory Activities (MedDRA)	25 or higher	
World Health Organization Drug Dictionary (WHODrug Global)	WHODrug-Global-B3 Sep 2021 or later	

3.2.7. ALS Functional Rating Scale - Revised (ALSFRS-R) score

The ALSFRS-R is a quickly administered (5-minute) ordinal rating scale that assesses the subjects' capability and independence in 12 functional activities across 4 subdomains of bodily function (bulbar, gross motor, fine motor, and respiratory) relevant in ALS. Each activity is recorded to the closest approximation from a list of 5 choices, scored 0 (total loss of function) to 4 (no loss of function), with the total score ranging from 0 to 48 and higher scores indicating less functional impairment (Cedarbaum 1999).

The score change from baseline will be calculated as the post baseline score minus the baseline score, so that a positive score for change from baseline would indicate improvement in function relative to baseline, while a negative score indicates worsened disease relative to baseline.

Subdomains	Items
Bulbar	Speech, Salivation and Swallowing
Fine Motor	Handwriting, Cutting Food/Handling Utensils and Dressing Hygiene
Gross Motor	Turning in Bed, Walking and Climbing Stairs
Respiratory	Dyspnea, Orthopnea and Respiratory Insufficiency
Scores for each ite rating)	em range from 0 to 4 (0 representing the worst/lowest functional rating and 4 the best

3.2.8. Pulmonary Function Tests

Pulmonary function tests are used to assess respiratory function. Pulmonary function tests (PFTs) will assess SVC and SNIP. Forced vital capacity, vital capacity, forced expiratory volume, and maximum inspiratory pressure will not be measured. Oxygen saturation (SpO₂), respiratory rate, and heart rate will be assessed in both upright and supine positions. The SNIP test will assess nasal pressure in each unilaterally occluded nostril during a maximal sniff to assess inspiratory muscle strength.

3.2.9. Modified Norris Scale

Modified Norris scale is used to assess the motor/limb and bulbar function. The Modified Norris Scale is a rating scale for ALS that consists of 2 parts: the Limb Norris Scale and the Norris Bulbar Scale. The Limb Norris Scale has 21 items to evaluate extremity function, and the Norris Bulbar Scale has 13 items to evaluate bulbar function. Each item is rated in 4 ordinal categories. The total score is calculated by summing all the scales (Norris 1974).

3.2.10. ALS Cognitive Behavioral Screen

The ALS CBS is a brief measure of cognition and behavior in patients with ALS. The ALS CBS is composed of 2 sections: cognitive and behavioral. The cognitive section includes commonly used elements of standard testing batteries, consisting of 8 tasks that assess attention, concentration, tracking/monitoring, and initiation and retrieval. Each subtest score ranges from 0–5 and the total score ranges from 0–20. The behavioral section is composed of questions sensitive to organic brain changes. It consists of fifteen 3-point Likert items (total score ranges from 0–45) questioning caregivers on patients' behavioral changes (3 = "no change"; 0 = "large change") and 4 "yes/no" questions on anxiety and depression.

3.2.11. ALSAQ-40 Assessment

The ALSAQ-40 is a disease-specific measure of health-related quality of life for ALS (Jenkinson 1999). It is specifically used to measure the subjective well-being of patients with ALS and provides scores for 5 scales: physical mobility (10 items: 1-10), activities of daily living and independence (10 items: 11-20), eating and drinking (3 items: 21-23), communication (7 items: 24-30) and emotional reactions (10 items: 31-40). If one of the question items of ALSAQ-40 is missing, the total score will be considered as a missing value. However, it may be included in the summary of the specific scales. Lower total scores for the ALSAQ-40 indicate better quality of life, with higher scores indicating poorer quality of life. Analyses will be performed on the total score.

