4.6. Multiplicity

A fixed sequence testing procedure will be employed for selected efficacy endpoints. If the primary endpoint is statistically significant at a 2-sided 0.05 level, the secondary endpoints will then be tested sequentially in the order listed below, each at a 2-sided 0.05 alpha level. Testing within the specified sequence will stop if a null hypothesis in the sequence fails to be rejected.

- (1) Change from baseline in ALSFRS-R at Week 24 in the ITT1 analysis population
- (2) Change from baseline in ALSFRS-R at Week 24 in the ITT2 analysis population
- (3) Subject ranks based on the CAFS at Week 24 in the ITT2 analysis population
- (4) Change from baseline in total score of the Amyotrophic Lateral Sclerosis Assessment Questionnaire (ALSAQ-40) after 24 weeks of treatment, in the ITT1 analysis population
- (5) Change from baseline in log transformed plasma NfL, in the ITT1 analysis population There will be no interim analysis.

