Day and month missing, year present	 Year different to year of first study drug dose: Impute day and month with "01JAN". Year same as year of first study drug dose: Impute month and day with same month and day as first dose of study drug. 	Impute day and month with "31DEC"

Partial Missing	Imputation for Start Date	Imputation for Stop
Start or Stop Date		Date
Month missing, day	Year different to year of first study drug dose:	Impute with "DEC"
and year present	Impute month with "JAN".	
	Year same as year of first study drug dose: Impute	
	month with same month as first dose of study drug.	
Caveats	If any imputed start date leads to a start date that is af	ter the stop date, then
	the start date will be imputed with the date of the stop	of AE.

ALSFRS-R incomplete / missing data

This section describes visit level imputations performed prior to the multiple imputation procedure.

If 1 item is missing within a domain (e.g. Bulbar), then the domain item will be inputted using the following formula:

Imputed domain score = mean of non-missing items multiplied by 3.

If item 12 on the ALSFRS score is missing, and the patient is not reported as having received non-invasive ventilation at the time of the visit (concomitant procedures CRFs) then item 12 will be imputed as a 4.

Total Score:

If a whole domain is missing or two items are missing, then the total ALSFRS-R total score will be imputed from the remaining 3 domains as the mean of all answered item scores in the 3 domains x 12. Total score will not be imputed if more than 1 domain has 2 or more missing items.

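### One blank item among 40 voids the ALSAQ-40 total tested at step 4 of the fixed sequence, and a blank at baseline can remove the subject from the model

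*SAP*

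**What the plan says.** Part A SAP, section 3.2.11, divides the ALSAQ-40 into five scales of 10, 10, 3, 7 and 10 items. On incomplete forms it says: "If one of the question items of ALSAQ-40 is missing, the total score will be considered as a missing value". The next sentence keeps a limited use for such a form: "However, it may be included in the summary of the specific scales". The section ends: "Analyses will be performed on the total score". Section 3.2.12 of the Parts B/C SAP has the same rule.

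Section 4.6 places this variable fourth after the primary endpoint: "Change from baseline in total score of the Amyotrophic Lateral Sclerosis Assessment Questionnaire (ALSAQ-40) after 24 weeks of treatment, in the ITT1 analysis population", at a two-sided 0.05 level. Plasma NfL follows it. Section 5.5.2 analyses it by an MMRM that has the baseline value of the endpoint as a covariate, also in interaction with time, and leaves missing totals to the model's implicit handling. Section 4.7, on missing data, deals only with the ALSFRS-R in the CAFS analysis.

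For the ALSFRS-R, Appendix 2 of the same SAP fills a single missing item within a domain: "Imputed domain score = mean of non-missing items multiplied by 3". If a whole domain is missing, it derives the total from the other three domains.

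**The concern.** The rule needs 40 answers out of 40 before a form counts in a formally tested analysis. The consequence depends on the visit.

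- **Baseline.** Protocol Table 1 schedules the ALSAQ-40 before dosing only on Day 1; there is no Screening assessment. Without a baseline total there is no change score at any visit and no covariate value, so the subject leaves the model. The MMRM does not impute a missing baseline.
- **Week 24.** Only that visit's total is lost. The subject stays in through Day 85, and the model recovers part of the information under MAR.

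At stake is the precision of step 4 and, because the sequence is fixed, the chance of reaching the NfL test. The SAP gives no reason for accepting up to 3 missing items of 12 on one scale (25%) and none of 40 on the other (one item is 2.5%).

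**Working it through.** **The plan's own figure.** The documents give no power, SD or item-missing rate for the ALSAQ-40. The only design figure is the primary endpoint's power of about 85%. A simulated joint rank test reproduces it: 205 versus 102 subjects, difference 2, SD 5.3, survival 96.5% and 95%, two-sided 0.05, giving 0.850. The point below does not depend on it.

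**Inputs from the documents.** Items: 10 + 10 + 3 + 7 + 10 = 40 (SAP 3.2.11). Part A assessments: Day 1, Day 85 and Day 169, plus early termination (Protocol Table 1). ITT1 size: 307 (SAP 1.5).

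**Assumption.** Each item is blank with probability q, independently across items and visits. The values of q are illustrative.

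**Formulas.**
- Total lost at one visit: m = 1 − (1 − q)^40.
- Subject removed for lack of a baseline total: m.
- Subject removed for lack of a baseline total or of both post-baseline totals: m + (1 − m)·m².

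| q | m per visit | m × 307 | Removed, either reason |
|---|---|---|---|
| 0.01% | 0.4% | 1 | 0.4% |
| 0.05% | 2.0% | 6 | 2.0% |
| 0.1% | 3.9% | 12 | 4.1% |
| 0.5% | 18.2% | 56 | 20.9% |
| 1% | 33.1% | 102 | 40.4% |

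Worked row, q = 0.5%: 0.995^40 = 0.818, so m = 0.182. Then m² = 0.033 and 0.182 + 0.818 × 0.033 = 0.209.

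**Precision.** If baseline losses fall at random in both arms, the standard error grows by about 1/√(1 − m): 1/√0.961 = 1.02 at q = 0.1%, and 1/√0.818 = 1.11 at q = 0.5%.

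**With half-scale proration.** A total is lost only if more than 5 of 10, 3 of 7 or 1 of 3 items are blank in some scale. Under the same assumption the loss per visit is about 0.007% at q = 0.5% and 0.03% at q = 1%.

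**The case against.** The strongest reply is that the size is unknown. No item-missing rate is documented, and very low rates are as compatible with the text as high ones. Blanks that cluster within a form or a person lose fewer totals than the formula gives. Collection is also favourable. The questionnaire belongs to in-person visits, is done before dosing, and stays mandatory if such a visit is held remotely (Protocol section 7 and Table 1 footnotes). Baseline procedures may be done in the 3 days before first dose. SAP 3.2.2 takes the last non-missing value within a week before first dose, unscheduled assessments included, so a blank noticed in time can be repaired. All of this stands. It limits the size but leaves the rule unchanged.

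The ALSFRS-R comparison also has limits. That scale is scored by a certified rater, its proration has a stopping rule, and accepting proration for one instrument does not establish it for another. The inconsistency calls for a reason, but it does not prove the ALSAQ-40 rule wrong.

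A reader might infer three stronger points that the documents do not support.

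- **A third of subjects drop out at q = 0.5%.** It is true that 1 − 0.995^80 = 33% would lack a baseline or a Week 24 total, but most of those missing only Week 24 remain in the model through Day 85.
- **The other 39 answers are wholly discarded.** They may still enter the descriptive scale summaries.
- **The treatment comparison is biased.** More disabled subjects may skip more items, but nothing in the documents shows this, and the rule is the same in both arms.

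**Conclusion.** The point holds as an avoidable loss of precision. One blank voids the total, no other section softens this, and an uncorrected blank on Day 1 takes the subject out of the step 4 analysis. Under independent skipping, between 0.4% (q = 0.01%) and 33% (q = 1%) of totals are lost per visit. At q = 0.5%, about 18% of subjects are removed for lack of a baseline total, or about 21% counting those with neither post-baseline total. These figures rest on assumed rates and on independence; clustering would lower them.

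The consequence is conditional. Step 4 is tested only after the primary endpoint and three secondary tests succeed, so the rule cannot affect the primary conclusion. Bias is possible but not shown.

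**What to change.** Before unblinding, amend section 3.2.11 of the Part A SAP and section 3.2.12 of the Parts B/C SAP. If at least half the items of a scale are answered, replace each missing item with the subject's mean of the answered items in that scale. Set the total to missing only if any scale falls below half. Keep the complete-item total as a sensitivity analysis. The half-scale threshold is a proposal of this review and is not taken from the documents.

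The cost is a few lines of SAP text and a short derivation. The downside is the assumption that skipped items resemble the answered items in the same scale; the sensitivity analysis shows how far the result depends on it. If blanks are rare, the two analyses will nearly coincide.
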